	Author(s): [name], [name]	Version: v3.1
	Dissemination level: public	

Study Title	DARWIN EU – EHDS Use Case: Natural history of coagulopathy in COVID-19 patients and persons vaccinated against SARS-CoV-2 in the context of the OMICRON variant
Protocol version identifier	V3.1
Date of last version of protocol	04/10/2023
EU PAS register number	EUPAS106679
Active substance	Covid-19 vaccines
Medicinal product	ChAdOx1, bnt162b2, Ad26.COVS.S, mRNA-1273
Research question and objectives	
Research question: The aim of the study is to contextualise the risk of venous and arterial thromboembolic events associated with COVID-19, during the Omicron period, and SARS-CoV-2 vaccination.
 
The research objectives which will be addressed incrementally to support the project aim are:
 
 1) To estimate the background incidence rate of venous and arterial thromboembolic events among the general pre-pandemic population. 2) To estimate the incidence rate of venous and arterial thromboembolic events among patients with COVID-19 within 30-, 60-, and 90- and 180-days during the Omicron period, stratified by prior SARS-CoV-2 vaccination and prior infection status. 3) To estimate the incidence rate of venous and arterial thromboembolic events among patients with SARS-CoV-2 vaccination within 30-, 60-, 90- and 180-days, , stratified by prior infection status. 4) To estimate a) the association between clinical risk factors including prior SARS-CoV-2 vaccination on the incidence rate of venous and arterial events among patients with COVID-19 and b) the impact that thromboembolic events have on worsening severity of COVID-19 during the Omicron period. 5) To estimate incidence rate ratios for venous and arterial thromboembolic events among patients with COVID-19 and people vaccinated against SARS-CoV-2, compared to the background

	Phase II C3-001 – Study Protocol	
	Author(s): [name], [name]	Version: v3.1
	Dissemination level: public	

	population using incidence rates estimated in objectives 1 to 3.
Country(-ies) of study	Spain, The UK, Germany, The Netherlands, and Estonian
Author	[name], [name]

	Phase II C3-001 – Study Protocol	
	Author(s): [name], [name]	Version: v3.1
	Dissemination level: public	

LIST OF ABBREVIATIONS

Abbreviation	Name
ATC	Anatomical Therapeutic Chemical Classification
EHDS	European Health Data Space
CDM	Common Data Model
COVID-19	Coronavirus disease-2019
DVT	Deep vein thrombosis
ECMO	Extracorporeal membrane oxygenation
EHR	Electronic Health Record
ENCePP	European Network of Centres for Pharmacoepidemiology and Pharmacovigilance
ICU	Intensive care unit
LPD	Longitudinal Patient Data
MACE	Major cardiovascular events
OMOP	Observational Medical Outcomes Partnership
SARS-CoV-2	Severe acute respiratory syndrome coronavirus 2
VTE	Venous thromboembolic events
ATE	Arterial thrombotic events
RT-PCR	Reverse transcription polymerase chain reaction
IRR	Incidence rate ratio
SIR	Standardized incidence rate ratio
CPRD	Clinical Practice Research Datalink
IPCI	Integrated Primary Care Information
SIDIAP	The Information System for Research in Primary Care
SNOMED	Systematized Nomenclature of Medicine
HIV/AIDS	Human immunodeficiency virus/ acquired immunodeficiency syndrome

	Phase II C3-001 – Study Protocol	
	Author(s): [name], [name]	Version: v3.1
		Dissemination level: public

	Phase II C3-001 – Study Protocol	
	Author(s): [name], [name]	Version: v3.1
	Dissemination level: public	

1. TITLE

DARWIN EU – EHDS Use Case: Natural history of coagulopathy in COVID-19 patients and persons vaccinated against SARS-CoV-2 IN the context of the OMICRON variant.

3. ABSTRACT (STAND ALONE SUMMARY OF THE STUDY PROTOCOL)

Title: DARWIN EU – EHDS Use Case: Natural history of coagulopathy in COVID-19 patients and persons vaccinated against SARS-CoV-2 IN the context of the OMICRON variant

Rationale and background: Coronavirus disease-2019 (COVID-19) patients are at increased risk of venous and arterial thromboembolic events. SARS-CoV-2 variants have evolved during the COVID-19 pandemic with the dominant variant being Omicron now (as of December 2021). Information relating to thromboembolic risk and its impact on COVID-19 largely relates to COVID-19 variants occurring earlier during the pandemic. Therefore, evidence used to contextualize coagulopathy risk in light of vaccination may now differ. There is a need to better understand the risks of thromboembolic events among patients with COVID-19 associated with the Omicron variant, their impact on prognosis, and whether risk factors for such events remain the same, overall and in the context of prior COVID-19 infection, SARS-CoV-2 vaccination and among certain subgroups.

This study is one of the five use cases selected in the pilot project to test and inform HealthData@EU frameworks. HealthData@EU pilot project is the European Health Data Space (EHDS) Pilot project that aims to investigate and establish an infrastructure and data ecosystem for the secondary use of health data to facilitate research, innovation and better policy making; and assess the ability to scale towards a Union-wide infrastructure, as a core component of the EHDS.

Objectives:

1. To estimate the background incidence rate of venous and arterial thromboembolic events among the general population pre-pandemic population.
2. To estimate the incidence rate of venous and arterial thromboembolic events among patients with COVID-19 within 30-, 60-, 90- and 180-days during the Omicron period, stratified by prior SARS-CoV-2 vaccination and prior infection status.
3. To estimate the incidence rate of venous and arterial thromboembolic events among patients with SARS-CoV-2 vaccination within 30-, 60-, 90- and 180-days, stratified by prior infection status.
4. To estimate a) the association between clinical risk factors and prior SARS-CoV-2 vaccination on the incidence rate of venous and arterial events among people with COVID-19 and b) the impact that thromboembolic events have on worsening severity of COVID-19 during the Omicron period.
5. To estimate incidence rate ratios for venous and arterial thromboembolic events among patients with COVID-19 and different SARS-CoV-2 vaccine doses compared to the background population, using incidence rates estimated in objectives 1 to 3.

Study type: population-level cohort

Study population:

- 1) Pre-pandemic cohort to calculate background rates of venous and arterial thromboembolic events in the general population (year 2017-2019).
- 2) People with COVID-19 during the time when OMICRON was the dominant variant (coded or test positive). All participants are required to be visible in the data source since 1st January 2020 to have full records on infection and vaccination history.
- 3) People vaccinated against SARS-CoV-2 (+/- during the period when OMICRON was the dominant variant). All participants are required to be visible in the data source since 1st January 2020 to have full records on infection and vaccination history.

For all cohorts, individuals with recent VTE or ATE event (defined as having a diagnosis of VTE or ATE within 183 days prior to index date, with sensitivity analysis of using any time prior and 91-days as wash-out periods.) will be excluded.

	Phase II C3-001 – Study Protocol	
	Author(s): [name], [name]	Version: v3.1
		Dissemination level: public

Analysis:

Standardized incidence rate ratio (SIR) compared to the background population will be estimated using indirect standardization.

Cohorts will be stratified by prior COVID-19 infection occurrence and prior SARS-CoV-2 vaccination (COVID-19 and vaccine cohorts only), age, sex. All cohorts will additionally be stratified by whether patients are immunocompromised on the index date.

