8.2 Study Setting and Data Sources

The selection of databases for this study was performed based on data reliability and relevance for the proposed research question among those databases onboarded and available within DARWIN EU. The selected databases fulfil the criteria required for the availability of key information on exposures, outcomes, and covariates, while covering different settings and regions of Europe.

Records on Covid-19 infection and vaccination (needed for objectives 2 to 5) will be available in all purposed databases except Estonia Biobank. We have previously published studies showing that these databases can generate reliable evidence on COVID-19 research. [20–22] Specifically, the availability of covid-19 tests results, and linked vaccination records through national/regional immunization program (SPRD, SIDIAP) increased the reliability of the identified study exposures. Inpatient admission and intensive care use (needed for objective 4) will be available in SIDIAP, which provides primary care records with linked hospitalization information.

Table 1. Description of the selected Data Sources.

Country	Name of Database	Justification for Inclusion	Health Care setting (e.g. primary care, specialist care, hospital care)	Type of Data (EHR, claims, registries)	Number of active subjects	Feasibility count of exposure (if relevant)	Feasibility count of disease (if relevant)	Data lock for the last update
Spain	SIDIAP	Complete records on SARS-CoV-2 infection, Covid-19 vaccination, and outcome events of interest; Include inpatient admission information. (objectives 1 to 5)	primary care database + linkage to hospital data	EHR	5.8M	Covid-19: 3865976, AstraZeneca :1152432, Janssen :257806, Pfizer :6548545, Moderna :3371395	VTE as example for all databases. 101966	1/6/2022
The UK	CPRD GOLD	Complete records on SARS-CoV-2 infection, Covid-19 vaccination,	primary care	EHR	3M	Covid-19: 360198, AstraZeneca	219844	07/2022

	Phase II C3-001 – Study Protocol	
	Author(s): [name], [name]	Version: v3.1
	Dissemination level: public	

Country	Name of Database	Justification for Inclusion	Health Care setting (e.g. primary care, specialist care, hospital care)	Type of Data (EHR, claims, registries)	Number of active subjects	Feasibility count of exposure (if relevant)	Feasibility count of disease (if relevant)	Data lock for the last update

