		and outcome events of interest (objectives 1 to 5, exclude 4b on worsening covid-19)				:2360815, Janssen :3034, Pfizer :2822947, Moderna :311069		
Germany	IQVIA Germany	Complete records on SARS-CoV-2 infection, Covid-19 vaccination, and outcome events of interest (objectives 1 to 5, exclude 4b on worsening covid-19)	outpatient visits of primary care physicians and a sample of specialists	EHR	8.5M	Covid-19:1723895, AstraZeneca :189261 , Janssen :83771 , Pfizer :2614482 , Moderna :428057	392674	1/9/2022
The Netherlands	IPCI	Complete records on SARS-CoV-2 infection, Covid-19 vaccination, and outcome events of interest (objectives 1 to 5, exclude 4b on worsening covid-19)	Primary care	EHR	1.39M	Covid-19: 941329, AstraZeneca :178192 , Janssen :19645 , Pfizer :1173104 , Moderna :463315	57087	1/12/2022

	Phase II C3-001 – Study Protocol	
	Author(s): [name], [name]	Version: v3.1
	Dissemination level: public	

Country	Name of Database	Justification for Inclusion	Health Care setting (e.g. primary care, specialist care, hospital care)	Type of Data (EHR, claims, registries)	Number of active subjects	Feasibility count of exposure (if relevant)	Feasibility count of disease (if relevant)	Data lock for the last update
Estonian	Estonian Biobank	Geographic representative (objective 1 only)	Biobank	EHR	0.2M	79411 (Covid-19)	25766	31/3/2021

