8.5 Study Population with inclusion and exclusion criteria

Five non-mutually exclusive study cohorts for the analyses will be defined:

- 1. General population cohort for pre-pandemic background rates** will have
 - Individuals will start contributing as of 1st January 2017, or when they have at least 365 days of data availability.
 - follow-up for this cohort will run up to 31 December 2019.
- 2. Persons tested positive for SARS-CoV-2 or with a clinical diagnosis of COVID-19 during the Omicron period** will
 - have either a positive test result for SARS-CoV-2 or a clinical diagnosis of COVID-19 on or after 1st December 2021 (with the index date being whichever date comes first if both occur)
 - have no positive test result for SARS-CoV-2 or clinical diagnosis of COVID-19 within 3 months prior to the index date.
 - have at least 365 days of data availability prior to index date
- 3. Persons hospitalised with COVID-19 during the Omicron period** will have
 - a hospitalisation on or after 1st December 2021 (with the index date the date of hospital admission),
 - a record of a clinical diagnosis of COVID-19 or a positive test result for SARS-CoV-2 in the period between 3 weeks prior to and up to 3 days following the index date.
 - have no diagnosis of COVID-19 or a positive test result for SARS-CoV-2 between 3 months and 3 weeks prior to index date.
 - have no COVID-19 hospitalisation within 3 weeks prior to the index date.
 - have at least 365 days of data availability prior to index date
- 4. Persons requiring intensive services during a hospitalisation with COVID-19 during the Omicron period** will have
 - intensive services initiated during a hospitalisation as described in cohort 3 (with the index date the date at which intensive services were initiated)
 - patients will have had a confirmatory diagnosis or test result of COVID-19 (both as defined above) within a time window from 3 weeks to their index date up to three days following their index date.
 - have at least 365 days of data availability prior to index date
- 5. Persons vaccinated against SARS-CoV2 infection**
 - a vaccination record identified by brand (with the index date the date of vaccination record)

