 - whether the vaccination record is 1st, 2nd, 3rd or 4th dose. A 21 day gap between two consecutive records of vaccine will be required to avoid repeated records of the same vaccine. The 21-days period was chosen based on the minimal recommended dosing schedule of the primary vaccine course in participated databases (Spain).
 - have at least 365 days of data availability prior to index date

Cohorts 2 to 5 will be stratified by prior COVID-19 infection status and for cohorts 2 to 4 also by prior SARS-CoV-2 vaccination status. All cohorts will additionally be stratified by whether patients are immunocompromised on the index date. People in each of the five cohorts will be required to have at least a year of observed history in the database prior to their index date. This is to ensure a sufficient time period to identify health conditions and medication use prior to individuals' index dates.

	Phase II C3-001 – Study Protocol	
	Author(s): [name], [name]	Version: v3.1
		Dissemination level: public

Table 3. Operational Definitions of Inclusion Criteria

Criterion	Details	Order of application	Assessment window	Care Setting ¹	Code Type	Diagnosis position ²	Applied to study populations:	Measurement characteristics/validation	Source for algorithm
Observation period of 365day prior entry (all 5 cohorts)	Study participants will be required to have 365 days prior history observed before contributing observation time	before	[-365,0]	n/a	n/a	n/a	All individuals within the selected databases	n/a	n/a
Covid-19 infection (cohort 2)	have either a positive test result for SARS-CoV-2 or a clinical diagnosis of COVID-19 on or after 1 st December 2021 (with the index date being whichever date comes first if both occur)	before	n/a	Primary care	SNOMED	n/a	All individuals within the selected databases	n/a	n/a
Covid-19 hospitalized (cohort 3)	a hospitalisation on or after 1 st December 2021 (with the index date the date of hospital admission), a record of a clinical diagnosis of COVID-19 or a positive test result for SARS-CoV-2 in the period between 3 weeks prior to and up to 3 days following the index date	before	[-21, 3]	Primary care, secondary care	SNOMED	n/a	All individuals within the selected databases	n/a	n/a

	Phase II C3-001 – Study Protocol	
	Author(s): [name], [name]	Version: v3.1
	Dissemination level: public	

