The included databases will vary in the data elements that they capture and in their current duration of follow-up. Depending on the dataset, not all study populations will be observed. For example, identifying the intensive services cohort will not be possible where inpatient hospital interventions are not observed. Similarly, not all outcomes may be available in all databases e.g. deaths. Some datasets may not capture COVID-19 diagnoses or tests occurring outside of hospital. Only the cohorts and outcomes that can reliably be identified will be assessed in the analyses. Since the vaccination programs changed over time (e.g. the primary vaccine courses targeted the general population, while the 4th dose were offered to more vulnerable people), the characteristics of patients receiving different doses may differ. However, we will stratify our analysis by prior vaccines whenever the power allows. It will also be assumed that vaccination recording is complete. Due to the availability of more recent data (CPRD is available until July 2022), some databases may have relative short follow-up time for study cohorts, and therefore may impact on the 90-days and 180-days incidence rates. The data elements that each data partner can provide will be detailed. The contextualisation of incidence rates using a historical background period assumes that coding practices and data recording are similar over time. However, this method has been used in previous studies focused on the 1st wave of covid, conducted by the same research group. [20,21] The analysis will calculate crude incidence rates and standardised incidence rates accounting for age and sex only. Differences in other potential confounders factors may exist and the characteristics of each cohort and stratification group will be inspected. No validation of outcomes using case note review will be performed.

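### The requirement that people be observable from 1 January 2020 stands only in the abstract; the operative criteria ask for 365 days, so infection, vaccination and dose history can be wrong in later entrants

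*Protocol*

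**What the plan says.** The abstract sets the same rule twice, once for people with COVID-19 in the Omicron period and once for vaccinated people: "All participants are required to be visible in the data source since 1st January 2020 to have full records on infection and vaccination history".

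Section 8.5 lists a different requirement under each of cohorts 2 to 5: "have at least 365 days of data availability prior to index date". It then repeats it for all cohorts: "People in each of the five cohorts will be required to have at least a year of observed history in the database". The reason given concerns comorbidity and drug history, not infection or vaccination: "This is to ensure a sufficient time period to identify health conditions and medication use prior to" the index date. Table 3 turns this into an inclusion criterion with the window [-365, 0]: "Study participants will be required to have 365 days prior history observed before contributing observation time".

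No other part of the protocol carries the 2020 date. Table X (section 7) and Table 2 mention 365 days only for the background cohort and give no look-back for the others. Table 4 has no criterion of this kind. Table 8, under missing data, limits cohorts 2 to 5 to people with complete exposure information, but names no date or window.

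On recording, section 11 says: "It will also be assumed that vaccination recording is complete". Section 8.2 says that "linked vaccination records through national/regional immunization program (SPRD, SIDIAP) increased the reliability of the identified study exposures", where SPRD is evidently CPRD.

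**The concern.** Prior infection and prior vaccination are the strata of objective 2, prior infection is the stratum of objective 3, and both are predictors in the Cox models of objective 4a and strata for the ratios of objective 5. Dose number (first to fourth) defines the groups within cohort 5 and is counted from records. Each of these needs history back to the start of the pandemic or of vaccination, which is the abstract's stated reason for the 2020 rule. One year of history does not supply it.

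A programmer works from section 8.5 and Table 3. Cohorts built that way include people whose record begins after 1 January 2020. An infection or dose before their entry is unseen, so they can be placed in the uninfected or unvaccinated stratum, and a third dose can be labelled a first. Cohorts built from the abstract would leave these people out. Two data partners could each follow the protocol and build different cohorts.

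**Working it through.** **Inputs.** Look-back origin 1 January 2020 (abstract). Minimum history 365 days (section 8.5, Table 3). First Omicron index date 1 December 2021 (section 8.3). Data locks from Table 1, read as day/month/year: SIDIAP 1 June 2022, CPRD GOLD July 2022, IQVIA Germany 1 September 2022, IPCI 1 December 2022. Estonian Biobank contributes to objective 1 only and is not affected.

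**Formula.** For index date D, the history that the abstract would guarantee is G = D − 1 January 2020. The history that section 8.5 guarantees is 365 days. The most that can be unseen is U = G − 365.

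| D | Guaranteed history starts | G (days) | U (days) | U/G |
|---|---|---|---|---|
| 1 Dec 2021 | 1 Dec 2020 | 700 | 335 | 48% |
| 1 Jun 2022 (SIDIAP lock) | 1 Jun 2021 | 882 | 517 | 59% |
| 1–31 Jul 2022 (CPRD lock) | 1–31 Jul 2021 | 912–942 | 547–577 | 60–61% |
| 1 Sep 2022 (IQVIA Germany lock) | 1 Sep 2021 | 974 | 609 | 63% |
| 1 Dec 2022 (IPCI lock) | 1 Dec 2021 | 1065 | 700 | 66% |

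These are maxima for a person who entered exactly 365 days before index. They are 0 for anyone present on 1 January 2020. The lock dates are the latest possible index dates in each database.

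**Prior infection.** U is 0 only for index dates up to 1 January 2020 + 365 days = 31 December 2020. Every Omicron index date is later, so prior infection is exposed throughout cohorts 2 to 4, and in cohort 5 for vaccinations after 31 December 2020.

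**Prior vaccination and dose number.** These are exposed once the index date lies more than 365 days after vaccination began. The protocol gives no start date. Assuming a start between 1 December 2020 and 1 March 2021, exposure begins for index dates after 1 December 2021 to 1 March 2022. Vaccine history that could be unseen is then 92–182 days at the SIDIAP lock and 275–365 days at the IPCI lock.

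**Share of the cohort affected.** This is (share entering after 1 January 2020) × (share of those with an infection or dose in the unseen window). Neither factor is in the protocol. Purely as an illustration, 2–15% late entrants and 5–30% with an unseen event give 0.02 × 0.05 = 0.1% to 0.15 × 0.30 = 4.5% of a cohort.

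**Side check on completeness (Table 1, four brands summed, per active subject).** SIDIAP 11,330,178/5.8M = 1.95; CPRD 5,497,865/3M = 1.83; IPCI 1,834,256/1.39M = 1.32; IQVIA Germany 3,315,571/8.5M = 0.39.

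**The case against.** The two rules are compatible. Anyone observable from 1 January 2020 has 365 days of history at any index date from 31 December 2020, so this can be read as a line not carried forward, with the abstract's intent clear. The Table 8 condition on complete exposure information points the same way. That is fair on intent, but it does not cure the gap: the condition sets no look-back, and the detailed criteria, which are what gets programmed, give a weaker rule with a different reason.

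The 365 days is also a minimum, and most people may have much longer records. This stands, and it limits the point to later entrants. Linked immunisation records in SIDIAP and CPRD might recover some doses given before entry, but the protocol does not say that they do, and they would not recover infections.

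The direction of bias is not fully certain. Individual errors run one way, from exposed to unexposed and from later dose to earlier dose. For a yes/no stratum this usually draws the strata together if the error is unrelated to outcome. For a four-level dose number that is not assured.

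**Conclusion.** The point holds as an internal inconsistency with a real but limited consequence. Under the operative criteria, people who entered a database after 1 January 2020 can lack up to 335 to 700 days of relevant history, depending on index date. Prior infection can be misclassified at every Omicron index date, and prior vaccination and dose number at later ones. The calendar figures rest on the protocol's own dates; the vaccination timing rests on an assumed start of roll-out. The size of the bias cannot be computed, because the share of late entrants is not given.

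A reader might infer more than this from two places, and the protocol does not support either reading.

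- That 11 months (at 1 December 2021) or 17 months (at 1 June 2022) of history is lost for the whole cohort. It is lost only for people who joined after 1 January 2020.
- That Table 1 shows about 20% vaccine capture in IQVIA Germany (0.39/1.95), that hazard ratios there will be attenuated accordingly, and that IQVIA Germany and IPCI should be kept out of pooled vaccine estimates. Table 1 does not say whether its counts are records or persons, or whether they relate to the active subjects. Lock dates and countries differ, and a ratio of counts is not a person-level sensitivity. Under-recording is also a separate matter, which the 2020 rule would not correct. The most that can be said is that 0.39 against 1.95 calls the section 11 assumption of complete vaccination recording into question.

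**What to change.** Add to section 8.5 and Table 3, for cohorts 2 to 5, that the observation period must start on or before 1 January 2020 and run to the index date, in addition to the 365-day rule. Repeat it in the population rows of Table X. Report per database how many people the rule removes. If the sponsor prefers to keep recent registrants, the abstract should drop the rule, and section 11 should state that infection, vaccination and dose history may be truncated in them.

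The cost is wording, one filter in code that section 5 still lists as to be confirmed, and the loss of recent registrants, including any child born after 1 January 2020. Section 8.7 sets no target size, so no sample-size calculation is disturbed.

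Separately, and at little cost, section 11 could present complete vaccination recording as something to be checked in each database, citing the spread in Table 1.
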